8.3 Randomization and Stratification

There will be no randomization. Subjects will be enrolled into one of the three cohorts described in the “General Design Issues” section above.

8.4 Sample Size and Accrual

8.41 Pharmacokinetics

Sample size for this study was estimated using a pharmacokinetic modeling and simulation approach. Details of this approach are provided in Supplemental Document I. Briefly, the objectives of this approach were to ensure that 1) the mean value of ETR apparent oral clearance (CL/F) has a standard error <20% on 80% of occasions and 2) that the 95% confidence interval for CL/F is 60 to 140% or 60 to 166.6% of the point estimate of the geometric mean on 80% of occasions in each of the above age groups. A third approach was developed and consisted of simulation-estimation platform incorporating data from previous trials. It was used to determine the number of pediatric subjects required across the age range of 2 months to <6 years to ensure the median estimate for CL/F for a typical subject within each age group has a reported standard deviation <20%. Based on a pharmacokinetic model adapted for pediatric maturation and incorporating prior data, a minimum of 12 subjects in each age group is deemed sufficient to provide pharmacokinetic data for pediatric subjects treated with ETR.

8.42 Safety

Total accrual will depend upon the number of subjects who must be accrued to yield a minimum of 36 evaluable subjects for purposes of the primary safety analyses. There is some uncertainty concerning the number needed to complete the dose finding procedures and the number who may be lost to follow-up for reasons other than treatment failure. Each successful age cohort will include at least 12 subjects. In total, it is anticipated that approximately 50 subjects may need to be enrolled in the protocol to yield 36 evaluable subjects for the weeks 24 and 48 safety analyses.

Table 7. Percent of Subjects Experiencing Grade 3+ Adverse Events (or Grade 3+ Adverse Events Attributed to the Study Medication) with Exact 95% Confidence Intervals

N	No. of Subjects (%) With Grade 3+ Adverse Events	95% C.I.
12	0 (0%)	0% -- 26%
24	0 (0%)	0% -- 14%
36	0 (0%)	0% -- 10%
12	1 (8%)	0.2% -- 38%
24	2 (8%)	1% -- 27%

36	4 (11%)	3% -- 26%
12	3 (25%)	5% -- 57%
24	6 (25%)	10% -- 47%
36	9 (25%)	12% -- 42%
12	4 (33%)	10% -- 65%
24	8 (33%)	16% -- 55%
36	11 (31%)	16% -- 48%

Table 7 presents exact 95% confidence intervals around various potential rates of Grade 3+ adverse events which might be observed in a total sample of 36 evaluable subjects, a sample of 12 subjects representing a minimal sample that might be accrued within any age stratum and potential sample size that might occur if a subgroup of N = 24 was analyzed. This table indicates that confidence intervals will be wide around the minimal sample size of 12 subjects within a given stratum, but would be reasonably precise around a sample size of 36 subjects.

8.5 Monitoring

The study will be monitored intensively by the core protocol team which will review safety and pharmacokinetic data at least twice a month during the dose-finding stage with the aim of determining the optimal dose for each cohort while protecting patient safety. In addition, the IMPAACT Network will appoint a study monitoring committee (SMC) to provide independent reviews when necessary to ensure subject safety. In accordance with IMPAACT and DAIDS procedures, this committee will be composed of two individuals from the Primary Scientific Committee, one PDMC member and a statistician, independent of both the P1090 protocol team and drug manufacturer (Janssen R&D). Members of said study monitoring committee will have:

- 1) No financial interest in the study;
- 2) No planned authorship in publication of study results; and
- 3) No involvement in the conduct of the study.

8.51 Safety Guidelines

8.511 Evaluation of the Starting Doses During the Dose-Finding Stage

The attribution of relationship of serious adverse events to study drug for the purposes of employing the start, stop and pause rules specified below will be by consensus among the site investigator, the protocol team and the DAIDS medical officers. If unanimous agreement between them cannot be established, the relevant data will be reviewed by the independent Study Monitoring Committee as described above, which will make the final judgment concerning the relationship between study drug and the adverse event. Within this committee the decision will be determined by the majority opinion of this study's independent Study Monitoring Committee clinicians.

Gradation of relationship will use the following terminology:

- Not related
- Probably not related
- Possibly related
- Probably related
- Definitely related

An event judged to be at least possibly related to the study treatment will be considered to be a Suspected Adverse Drug Reaction (SADR) for purposes of the dose finding algorithm which follows.

8.512 First Six Subjects Started at a Given Dose Level in Each Cohort

For each study cohort (Cohort I, Cohorts II & III combined), the frequency of adverse reactions to the starting dose of the study medication will be evaluated on the first 6 subjects. The data will extend to the week 4 visit for subjects not requiring dose adjustment or until the visit on which the dose is adjusted, as described above. Further accrual into this cohort will be contingent upon meeting the following safety guidelines:

If any of the first 6 subjects has a life threatening SADR or any Grade 4 event or death that is probably or definitely attributable to the study medication or 3 or more subjects have terminated study drug due to a Grade 3+ at least possibly treatment related SADR, stop accrual into this study cohort (Cohort I, Cohorts II & III combined) until a safety review by the P1090 core protocol team is conducted. If none of the first 6 subjects has experienced a life-threatening SADR or a Grade 4 event or death that is probably or definitely attributable to the study medication and at most 2 of these 6 subjects has terminated study drug due to a Grade 3+ at least possibly treatment related SADR, then this cohort has passed the initial safety guidelines. If these 6 subjects also meet the PK guidelines, accrue more subjects to this cohort and evaluate the safety and PK results of the overall cohort.

In cases where the mini-cohort has failed either the safety or pharmacokinetic guidelines, the P1090 core protocol team will conduct a thorough review before proceeding with accrual to the study. All of the relevant safety and pharmacokinetic data will be examined to determine whether it is safe to continue the attempt to find an optimal dose for this cohort. If the P1090 study team determines that it is safe to proceed, it will make specific changes in dosing and monitoring procedures which may be indicated. If there are any concerns regarding safety, the study's Study Monitoring Committee will then review all of the relevant safety and pharmacokinetic data, along with the recommendations of the core protocol team, and will determine whether and under what conditions further dose finding activities for this cohort may proceed.

The protocol will only proceed if this review has led to a recommendation that it is safe to do so. The safety review may lead to a recommendation that the dose be de-escalated. Before implementing such a recommendation, the P1090 core protocol team will review the PK data to determine whether a lower dose is likely to achieve adequate drug exposure.

Given the small sample sizes within each cohort, the information available for preliminary safety decisions will be imperfect. Two types of sampling errors are possible: 1) in a cohort where the true rate of toxicity is too high to warrant increased exposure to the current starting dose of the medication, the sample data may pass the safety guidelines; and 2) in a cohort where the true rate of toxicity is low enough that further

exposure to the current starting dose is warranted, the sample data may fail the guidelines.

The extent to which the safety guidelines protect against the errors described above can be assessed by examining various hypothetical rates of "true toxicity" which could occur, if the study medication were used extensively among the patient population at the dose level under question. The hypothetical situations presented in the immediately succeeding table range from conditions under which a given dose level would cause a high incidence of severe and life threatening SADRs to conditions under which severe SADRs would be relatively rare and would not be life threatening. For each of these hypothetical situations, we assume that a sample of 6 subjects is drawn from the patient population and that the safety guidelines, summarized above, are followed.

Table 8 shows that there is a 78% chance of failing the safety guidelines under conditions in which the true rate of life-threatening toxicity is 5% and the rate of non-life threatening SADR is 50%. Assuming that it would be undesirable to accrue additional subjects at a dose that had these true rates of adverse events, the 22% chance of NOT failing the safety guidelines would represent the probability of error. The table also shows that there is a 0.2 % chance of failing, when the true rate of non-life threatening SADR is only 5% and the true rate of life threatening SADR is zero. Assuming that the potential benefits associated with exposing additional subjects to this dose of the drug would outweigh the risks associated with this relatively low rate of toxicity, failing the safety guidelines under these conditions would be an error.

Table 8. Probability of Failing Dose Escalation Guidelines under Potential Rates of True Toxicity

True Toxicity Rates		Probability of Failing Safety Guidelines
Non-Life Threatening SADR that would result in treatment discontinuation, excluding Grade 4 events probably or definitely attributable to study medication	Life Threatening SADR or Grade 4 events probably or definitely attributable to study medication	
0.50	0.00	0.67
0.50	0.05	0.78
0.50	0.25	0.98
0.25	0.00	0.17
0.25	0.05	0.41
0.25	0.25	0.88
0.05	0.00	0.002
0.05	0.05	0.27
0.05	0.25	0.82
0.00	0.05	0.26
0.00	0.25	0.82

8.513 Total Group of Subjects (Minimum of Twelve) Started at a Given Dose Level of Each Cohort

The final safety guidelines applied to a given starting dose of the study medication within a cohort will make use of data from all subjects started at that dose. The data will extend to the week 4 visit for subjects in the cohort which do not require PK determined dose adjustments or until the visit on which the dose is adjusted, as described above. If none of these subjects has experienced a life-threatening SADR or a Grade 4 event or death that is probably or definitely attributable to the study medication and no more than 25% terminated study treatment due to Grade 3+ at least possibly treatment related SADR, then this starting dose will pass the safety guidelines for the cohort under investigation.

If any of these subjects has a life threatening SADR or any Grade 4 event or death that is probably or definitely attributable to the study medication or more than 25% terminated study treatment due to Grade 3+ at least possibly treatment related SADR, this starting dose will fail the safety guidelines for the cohort under investigation. If this occurs, the core protocol team will review all of the relevant safety and pharmacokinetic data in an attempt to determine whether it is safe to continue the attempt to find an optimal dose for the said cohort.

If the P1090 study team determines that it is safe to proceed, it will make specific changes in dosing and monitoring procedures which may be recommended. If there are any concerns resulting from an inconclusive safety/PK study team review, the study's independent Study Monitoring Committee will then review all of the relevant safety and pharmacokinetic data and will determine whether and under what conditions further dose finding activities for this cohort may proceed.

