8.52 Study Safety Monitoring

Since Phase I and Phase II studies are not routinely reviewed by a Data and Safety Monitoring Board (DSMB), it is the responsibility of the Protocol Team to interpret safety data, and make decisions regarding SADRs that are needed to protect subjects from undue risk. In addition, the Study Monitoring Committee described above is appointed to provide impartial reviews in situations where patient safety is in question.

For safety monitoring, a drug related SAE is an SAE that is judged to be “definitely”, “probably” or “possibly related” to study drug (ETR).

The safety and tolerability of the study agent will be monitored by means of adverse events reports and toxicity reports presenting laboratory and clinical events. It is required that the data required for the toxicity reports be entered into the database within 48 hours of the time at which the results of the laboratory tests or clinical examinations become available.

Reports compiled by the Data Management Center (DMC) will be reviewed and discussed by the Protocol Team on conference calls held at least twice a month during the dose-finding stage and every month thereafter and by the study’s Study Monitoring Committee under conditions specified above. Data on accrual, pharmacokinetics and toxicity will be reviewed.

Adverse events will be monitored from screening onwards throughout the follow-up period. If the protocol team identifies any potentially treatment-related toxicities, which may compromise subject safety, the study will be paused and the Study Monitoring Committee will review all relevant data and will determine whether, and under what conditions, the study would be allowed to proceed.

8.521 Rules for Suspending Accrual to Assess Safety Following an Adverse Event

Accrual will be temporarily suspended if any subject has a life threatening Suspected Adverse Drug Reaction (SADR), or death, or any Grade 4 event that may not be judged to be life- threatening but is judged to be probably or definitely attributable to the study medication.

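### As worded, Sections 8.512 and 8.513 require stronger drug attribution for a death than for a survived life-threatening event, so one possibly related death would be recorded as a pass

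*Protocol*

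**What the plan says.** Protocol 8.511 sets a five-step scale of relationship to study drug and fixes the SADR threshold at its middle step: "An event judged to be at least possibly related to the study treatment will be considered to be a Suspected Adverse Drug Reaction".

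Protocol 8.512 covers the first six children at a dose. Accrual to the cohort stops if any child "has a life threatening SADR or any Grade 4 event or death that is probably or definitely attributable to the study medication", or if "3 or more subjects have terminated study drug due to a Grade 3+ at least possibly treatment related SADR". The matching pass sentence begins "If none of the first 6 subjects has experienced a life-threatening SADR or a Grade 4 event or death that is probably or definitely attributable" and allows at most two such terminations.

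Protocol 8.513 applies the same structure to everyone started at the dose, with a minimum of twelve: "If any of these subjects has a life threatening SADR or any Grade 4 event or death that is probably or definitely attributable", or if "more than 25% terminated study treatment due to Grade 3+ at least possibly treatment related SADR, this starting dose will fail the safety guidelines". Its pass sentence attaches the same attribution condition to death.

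Both rules use data to the week 4 visit, or to the visit at which the dose is adjusted.

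Protocol 8.521 is a separate, study-wide rule: "Accrual will be temporarily suspended if any subject has a life threatening Suspected Adverse Drug Reaction (SADR), or death, or any Grade 4 event". There the probable-or-definite condition follows the Grade 4 event only; death stands without one. The Study Monitoring Committee then reviews within 48 hours of notification.

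Table 8 gives the chance that six children fail. It has one column for non-life-threatening SADRs leading to discontinuation and one for life-threatening SADRs or probably or definitely attributable Grade 4 events. Neither heading mentions death.

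**The concern.** Any child's life-threatening SADR fails the rule, and possible relation is enough to make an event a SADR. In all four pass and fail sentences of 8.512 and 8.513, death is tied to the stricter probable-or-definite condition. The worse outcome therefore needs the stronger attribution.

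Two other parts of the protocol treat the matter differently. Section 8.52 counts an SAE as drug-related for monitoring when it is possibly, probably or definitely related, and 8.21 lists death as a primary toxicity endpoint with no attribution condition.

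What is at stake is the recorded status of the dose. Section 8.61 and SAP 6.2 report which starting doses passed or failed the safety guidelines, and 8.1 makes younger children's exposure depend on the older cohort having passed. A failed first-six rule brings a core-team review before the protocol may proceed; a failed full-cohort rule means that the starting dose itself fails. Neither follows from a pass.

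**Working it through.** **1. The two events side by side.** Suppose one child has one event, rated possibly related, and nothing else happens in the cohort.

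| Step | Life-threatening, survived | Death |
|---|---|---|
| SADR under 8.511? | Yes | Yes |
| Named in the single-event clause at this attribution? | Yes, as a life-threatening SADR | Not by name; death is listed with a probable-or-definite condition |
| Count toward the termination clause | Not needed | At most 1 (limit 2 of 6; 25% of 12 = 3) |
| Result, 8.512 | Fails | Passes |
| Result, 8.513 | Fails | Passes |
| Accrual suspended under 8.521? | Yes | Yes |

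**2. Reproducing Table 8.** Let *a* be the rate in the first column and *b* the rate in the second, as mutually exclusive outcomes in six children. The rule passes with no *b*-event and at most two *a*-events, so

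P(fail) = 1 − Σ (x = 0 to 2) C(6, x) · a^x · (1 − a − b)^(6 − x).

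- a = 0.50, b = 0.05: 1 − (0.0083 + 0.0554 + 0.1538) = 0.783; Table 8 has 0.78.
- a = 0.05, b = 0: 1 − (0.7351 + 0.2321 + 0.0305) = 0.0022 from unrounded terms; Table 8 has 0.002.
- a = 0, b = 0.05: 1 − 0.95^6 = 0.265; Table 8 has 0.26.

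All 11 rows agree within 0.02. The largest gap is in the first row, 0.656 against 0.67; the rest agree within 0.005. The table follows from the stated rule, and nothing here disputes its figures.

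**3. What the column means for an event.** The last two rows checked carry the same 5% rate in different columns. In the single-event column, six children fail with probability 0.26. In the termination column, they fail with probability 0.002. For twelve children, the same comparison is 1 − 0.95^12 = 0.46 against P(at least 4 of 12) = 0.002.

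**4. Range.** The documents give no rate of possibly related death for these children, so the rate *q* is an assumption. With no other events, the chance of failing is:

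| q | n = 6, single-event trigger: 1 − (1 − q)^6 | n = 6, termination only: P(≥ 3) | n = 12, single-event trigger: 1 − (1 − q)^12 | n = 12, termination only: P(≥ 4) |
|---|---|---|---|---|
| 1% | 0.06 | 0.00002 | 0.11 | < 0.0001 |
| 2% | 0.11 | 0.00015 | 0.22 | 0.00007 |
| 5% | 0.26 | 0.002 | 0.46 | 0.002 |
| 10% | 0.47 | 0.016 | 0.72 | 0.026 |

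The termination-only columns take a death to count as a termination, which the protocol does not state. If it does not count, those entries are zero. They also ignore the suspension under 8.521, so they show what the column choice does rather than forecast the trial.

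**The case against.** **A fatal reaction is already life-threatening.** This is the strongest reply. A possibly related event that kills a child meets the SADR definition and would ordinarily be called life-threatening, so the first limb would catch it. Table 8 gives some support, since a fatal SADR cannot sensibly sit under a non-life-threatening heading. But this reading leaves the separate mention of death with almost no work to do, and the protocol nowhere adopts it. What stands is that the rule can be read two ways with opposite results.

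**The probable-or-definite condition might cover the life-threatening SADR too.** That would remove the asymmetry, but it would leave the 8.511 threshold without effect in this clause. Table 8 and 8.521 both keep the life-threatening SADR apart from the attributable Grade 4 event. It is the weakest reading.

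**Section 8.521 already handles deaths.** Largely true, and it limits the consequence. Every death suspends accrual, and accrual resumes only if an independent committee thinks the drug likely to be safe for further children. A broad suspension rule beside a narrower dose rule can also be deliberate layering. However, 8.521 decides whether accrual resumes, and says nothing about whether the dose passed.

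**A pass does not hide a death or settle the dose.** Also true. Death is a primary endpoint, SAP 6.1 lists all deaths with etiologies, and the core team must still approve the dose. Failing 8.512 stops accrual for review; it does not reject the dose automatically.

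**Conclusion.** The point holds as an inconsistency in the dose-acceptance wording. Taken literally, one possibly related death within the evaluation window, with no other event, is recorded as a pass under both 8.512 and 8.513, where a survived life-threatening event with the same attribution is recorded as a failure. This rests on not reading a fatal reaction as a life-threatening SADR, a question that the text leaves open. For scale, Table 8's own contrast at an illustrative 5% is 0.26 against 0.002.

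Three stronger conclusions that a reader might draw are not supported:

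- **That such a death would escape review.** Section 8.521 requires suspension and independent review.
- **That two of six or three of twelve children could die with the dose still passing.** This assumes that a death counts as a termination, which is not stated, and that accrual is allowed to resume after each committee review.
- **That possibly related is the likely rating for a death in these children.** No source is given. The 8.511 scale has two lower steps, and in the pooled adult data in Section 1.32, 25 of 26 deaths on etravirine were rated not or unlikely related and one possibly related. The trial in ages 6 to 17 reported no deaths.

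**What to change.** Reconcile the attribution level for death in the pass and fail sentences of 8.512 and 8.513 with the SADR definition in 8.511 and with 8.521, so that a death is not held to a stricter attribution bar than a survived life-threatening event. In the Table 8 headings, name the column in which deaths are counted; this also settles whether a death can enter as a termination.

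The change touches four sentences and the table headings. The Table 8 probabilities stay as they are, because they depend only on the assumed rates in each column. The downside is that a possibly related death would also count as a failure of the guidelines, adding the core-team review to the suspension and committee review that 8.521 already requires.

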Initial tests of safety and PK will examine data from the first 6 subjects (mini-cohort) of Cohort I to determine whether Cohort II and Cohort III will be allowed to open for its mini-cohort of 6 subjects. Subjects below 6 months of age will not be enrolled until there are initial safety and PK data from subjects between 6 months and 1 year of age. These tests will proceed as follows:

- The PK data for the first six subjects of the Cohort I will be evaluated on the basis of blood samples taken 14 days \pm 4 days after the start of therapy.
- Safety will be evaluated on the basis of all available data collected through the 28th day on the dose that is being evaluated (see Section 8.51 for the safety guidelines to be used in the dose-finding algorithm).
- For subjects failing to meet PK targets and requiring individual dose adjustments, safety will be evaluated on the basis of data gathered until the time of the visit at which the dose is adjusted. This will insure that, for subjects needing PK determined dose adjustment, adverse events attributed to the starting dose must have occurred while the subjects were still on that dose. However, this also means that for such subjects the safety of the starting dose may be assessed on the basis of less than 28 days of study drug exposure.

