8.6 Analyses

8.61 Summary of Dose Finding Data

The analysis of dose finding data will consist of descriptive statistics summarizing the safety and PK data from the dose finding phase of the study. (See Section 9.0 for PK analysis). The safety data will be analyzed by cohort and will present the results of the safety evaluations applied to each starting dose regimen tested within each cohort, including information indicating which starting doses have passed or failed the safety guidelines. For each starting dose within each cohort, every adverse event of Grade 3 or higher will be listed, along with subject demographics, the dose prescribed to the patient at the time of the event and the protocol team's assessment of the probability that this event was due to the study treatment (not related, probably not related, possibly related, probably related or definitely related).

8.62 Analysis of Data Representing Exposure to the Doses Judged to be Optimal for Each Cohort

These analyses will be stratified by cohort. The findings will be presented in both in aggregate and broken down by cohort, with estimates bounded by 95% confidence limits. Given that the small sample sizes within cohorts will provide limited power for statistical tests of differences across age cohorts, interpretation of the results will depend upon whether differences across cohorts are great enough to be considered to be clinically significant. If no such differences are observed, then the clearest interpretation of the findings will come from the aggregated data, where analyses will have the greatest statistical precision. However, if results vary across cohorts to a clinically important extent, interpretation of results should take into account the issues represented by the stratification factor.

8.63 Primary Analyses - performed on data through the Week 24 and Week 48 visit

8.631 Safety

The primary safety analysis will include only subjects whose total exposure to ETR has been at the dose judged to be optimal for their cohorts. Subjects whose doses have been adjusted for inadequate PK will be excluded. Subjects who have been removed from treatment or have had their doses reduced due to toxicities while on the optimal dose will be included and treated as safety failures in the primary safety

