9.34 Individual Subject Dose Evaluation and Adjustments

Doses of ETR will be adjusted in an individual subject to attain an AUC_{12h} of $< 2350 \text{ ng}\cdot\text{h}/\text{mL}$.

- If the subject's current dose is well tolerated (no toxicity \geq Grade 3) but AUC_{12h} is $< 2350 \text{ ng}\cdot\text{h}/\text{mL}$, then a new dose will be determined by prorating the current dose to attain an AUC_{12h} of approximately $2864 \text{ ng}\cdot\text{h}/\text{mL}$ (the 20th percentile of exposure in adults). The maximum dose increase for the initial PK-guided dose adjustment would be capped at the adult dose of 200 mg twice daily. If a second PK evaluation again reveals an $AUC_{12h} < 2350 \text{ ng}\cdot\text{h}/\text{mL}$, then the dose may be increased above the 200 mg twice daily initial BID cap, again, targeting an AUC_{12h} of approximately $2864 \text{ ng}\cdot\text{h}/\text{mL}$.
- If the subject's AUC_{12h} is $> 4380 \text{ ng}\cdot\text{h}/\text{mL}$ (the median AUC_{12h} value in adults receiving ETR 200 mg twice daily) but current dose is not well tolerated (no toxicity \geq Grade 3) then the dose will be prorated, if possible given available dosage forms to achieve an AUC_{12h} of $4380 \text{ ng}\cdot\text{h}/\text{mL}$. If no dose reduction is possible, then the subject will be discontinued from study treatment.
- If a subject has not achieved an AUC_{12h} of $< 2350 \text{ ng}\cdot\text{h}/\text{mL}$, but is experiencing a Grade 3 or greater toxicity that is deemed probably or definitely related to study drug, that subject will be discontinued from study treatment.

Although ETR displays non-proportional PK, dose adjustments will be prorated on a linear scale using multiples of 12.5 mg (the smallest incremental dose change possible given the available formulations).

Initial PK-guided dose increases will be capped at the adult dose of 200 mg twice daily. However, if after a second PK evaluation the subject's AUC_{12h} has not achieved the minimum target (2350 ng•h/mL), doses may exceed 200 mg twice daily. The core protocol team will communicate all individual dose adjustments to the participating site.

All subjects with an individual dose adjustment (not related to weight gain) will have repeat intensive 12 hour PK evaluations performed between Day 7 to 14 after initiation of the new dose.

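### The starting-dose safety rule in 8.512/8.513 counts terminations and severe events but not toxicity-driven dose reductions, which 8.631 scores as safety failures

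*Protocol*

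**What the plan says.** The safety rule for a starting dose has two limbs.

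- **Severe-event limb.** The dose fails if any child "has a life threatening SADR or any Grade 4 event or death that is probably or definitely attributable to the study medication". This applies whether or not drug was stopped.
- **Termination limb.** In the mini-cohort (8.512), accrual stops if "3 or more subjects have terminated study drug due to a Grade 3+ at least possibly treatment related SADR". The dose passes this limb if "at most 2 of these 6 subjects has terminated study drug due to a Grade 3+ at least possibly treatment related SADR". In the full cohort (8.513) it passes if "no more than 25% terminated study treatment due to Grade 3+ at least possibly treatment related SADR".

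For a child whose dose is adjusted, 8.512 runs the data only "until the visit on which the dose is adjusted, as described above". Section 8.1 states the same cut-off for children who miss PK targets: "safety will be evaluated on the basis of data gathered until the time of the visit at which the dose is adjusted".

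Section 9.34 provides a reduction route. If AUC12h exceeds 4380 ng·h/mL and the dose is not well tolerated, "then the dose will be prorated, if possible given available dosage forms"; the child is discontinued only if no reduction is possible. Section 6.8 also refers to children above 4380 whose dose cannot be reduced.

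The primary safety analysis in 8.631 deals with such children explicitly: "Subjects who have been removed from treatment or have had their doses reduced due to toxicities while on the optimal dose will be included", and they are scored as safety failures.

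**The concern.** A child taken off the starting dose for toxicity is evidence against that dose whether the next step is a lower dose or no drug. The termination limb sees only the second case. If the dose is lowered for a Grade 3 SADR, or for a Grade 4 SADR that is not life-threatening and is judged only possibly related, the child stays in the denominator and never enters the numerator. If the data cut-off is applied to that child, a later termination on the lower dose falls outside the rule as well.

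The rule that accepts a dose and the analysis that describes its safety therefore treat the same child differently, and the protocol gives no reason. At stake is how far the rule protects the next six children, and the younger cohorts, from a dose that many cannot stay on.

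**Working it through.** **1. Which children are missed.** Three sections govern a child with a related Grade 3 event, and they disagree.

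- 6.8 lists Grade 3 or higher events thought related or possibly related to study drug among the criteria that lead to discontinuation. The child would be counted.
- 6.12 withholds ETR for a confirmed, at least possibly related Grade 3 event and allows restart if it settles to Grade 2 or lower within 21 days. The child has not terminated and is not counted.
- 9.34 prorates the dose above 4380 ng·h/mL. The child is not counted. Its trigger asks for a dose that is not well tolerated, yet its parenthesis specifies the absence of Grade 3 or higher toxicity. The first bullet of 9.34 uses that same parenthesis to define a well-tolerated dose, so the second bullet contradicts itself.

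**2. Extreme counts.** Two terminated plus four reduced for Grade 3 SADRs is 6 of 6 affected, and the mini-cohort passes. Three terminated plus nine reduced is 12 of 12 affected, and the full cohort passes, because 3/12 = 25% is not more than 25%.

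**3. Reproducing Table 8.** Let a be the rate of SADRs leading to discontinuation and b the severe-event rate, as mutually exclusive outcomes:

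P(fail) = 1 − Σ(x = 0 to 2) C(6,x) · a^x · (1 − a − b)^(6−x)

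For a = 0.50 and b = 0.05: 1 − (0.0083 + 0.0554 + 0.1538) = 0.783, against 0.78 in the table. All 11 rows agree within 0.02; the largest gap is 0.656 against the stated 0.67 at a = 0.50, b = 0. Treating the two outcomes as independent gives 0.747 for the 0.78 row and misses four rows, so the exclusive form is the one the table uses.

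**4. Effect of uncounted reductions.** Let t be the true rate of non-life-threatening Grade 3+ SADRs outside the severe-event limb, and f the share of those children who are reduced rather than terminated. Then a = t(1 − f). The documents give no value for f, so a range is shown. The rule fails at 3 or more of 6, and at 4 or more of 12.

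| n | t | b | f = 0 | 0.25 | 0.50 | 0.75 | 1 |
|---|---|---|---|---|---|---|---|
| 6 | 0.50 | 0 | 0.66 | 0.40 | 0.17 | 0.03 | 0.00 |
| 6 | 0.50 | 0.05 | 0.78 | 0.59 | 0.41 | 0.29 | 0.26 |
| 12 | 0.50 | 0 | 0.93 | 0.72 | 0.35 | 0.05 | 0.00 |
| 12 | 0.50 | 0.05 | 0.97 | 0.87 | 0.67 | 0.49 | 0.46 |
| 6 | 0.25 | 0 | 0.17 | 0.08 | 0.03 | 0.00 | 0.00 |
| 12 | 0.25 | 0 | 0.35 | 0.17 | 0.05 | 0.01 | 0.00 |

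If reductions were counted with terminations, the f = 0 column would apply whatever f is.

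**5. A low rate.** Protocol 1.32 reports Grade 3 or 4 adverse events of any cause in 14.6% of children in PIANO over 48 weeks. With t = 0.146, b = 0 and n = 6, P(fail) = 1 − (0.388 + 0.398 + 0.170) = 0.044 at f = 0. At f = 0.50, a = 0.073 and P(fail) = 1 − (0.635 + 0.300 + 0.059), or about 0.007.

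**6. Text against table.** The prose before Table 8 attaches the 78% to a 50% rate of non-life-threatening SADRs in general. The column heading restricts that rate to SADRs that would lead to discontinuation. The two agree only if no affected child is reduced or restarted.

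**The case against.** The strongest reply is that the missed group may be empty. If 6.8 is always followed, every child with a related Grade 3+ event stops drug and is counted. Grade 3 rash (6.13), Grade 3 allergic reactions (6.14) and centrally confirmed Grade 3 ECG changes (6.15) have their own discontinuation rules, and 1.4 names rash as the main treatment-limiting event. Section 6.12 also discontinues confirmed Grade 4 events unless they are judged unrelated or the team agrees that withholding drug would be harmful, so the gap is mainly about Grade 3. Read literally, the 9.34 parenthesis excludes Grade 3+ children from reduction altogether. All of this stands as a reason f may be small. It does not remove the point, because 9.34, 6.8 and 8.631 all presuppose that toxicity-driven reductions or their alternatives arise, and nothing says which section prevails.

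Several stronger readings are tempting, and the documents do not support them.

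- A reader might infer that only terminations count. The severe-event limb fails the dose regardless of what happens to dosing.
- A reader might infer that a reduced child is recorded as tolerating the dose. No text says so: the child is simply not counted against it. Section 9.351 separately requires a tolerated dose, though without defining it.
- A reader might infer that Table 8 is wrong. It reproduces, and its column is already limited to SADRs leading to discontinuation.
- A reader might take f to be about one half because 4380 is the adult median. Being above 4380 does not mean being reduced, and 1.31 reports no correlation of adult exposure with adverse events.
- A reader might take the 8.631 definition as interchangeable with that of the rule. It has no grade or relatedness condition and covers 24 and 48 weeks, against about 4.

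Two further limits stand. The cut-off in 8.1 and 8.513 is written for PK-driven adjustments, so its use for a reduction prompted by both exposure and toxicity is unclear. And team review at least twice a month (8.5), with the pause provision in 8.52, is a real backstop, though not a prespecified count.

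**Conclusion.** The point holds in a limited form. The termination limb leaves out dose reductions for Grade 3 SADRs and for non-life-threatening Grade 4 SADRs judged only possibly related, while the primary safety analysis counts toxicity-driven reductions as failures. Hold-and-restart under 6.12 escapes the count in the same way. Whether a child counts against a dose can therefore depend on which of three conflicting sections is followed.

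The size depends on two quantities. The true SADR rate is unknown, and the reduced share f is an assumption with no figure in the documents. At a 50% rate the loss of protection is large even for f = 0.25. Near 15% the chance of failing is already low, so the change is a few percentage points. The calculation also assumes independent children and mutually exclusive outcomes, as Table 8 does.

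**What to change.** 1. Reconcile 6.8, 6.12 and 9.34, including the 9.34 trigger, so that one rule governs a child with a related Grade 3+ event. Which clinical rule is right is for the protocol team and is not judged here.
2. In the pass and fail sentences of 8.512 and 8.513, count a child who terminated study drug or had the starting dose reduced because of a Grade 3+ at least possibly related SADR. State how a hold followed by restart is counted, and whether the data cut-off applies to a reduction made for toxicity.
3. Give the sentence quoting the 78% and the first column label of Table 8 that same definition. The table's probabilities need no recalculation, because they are indexed by the rate of counted events.
4. Show terminations and reductions separately at each safety review.

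The cost of the counting change is four protocol sentences, one sentence of text and a column label. It changes how a child is counted, not how any child is treated. The rule becomes slightly stricter: if no child is reduced its result is unchanged, and otherwise some doses that would now pass go to the core-team review that 8.512 and 8.513 already prescribe.
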